2.5. What are the proposed methods of protecting against sources of bias?

A centrally controlled computerised randomisation service will be used. It is not possible to mask physicians or patients to the interventions allocated or undertaken. Outcomes have been defined to be as objective as possible. Centres will be asked to provide copies of case notes, autopsy reports, and laboratory reports, to document primary outcomes. An adjudication subcommittee of the Steering Committee will review the neonatal data for all babies in the study, blinded to group of allocation and actual method of delivery, to determine if the criteria for the primary outcome have been met.

2.6. What is the proposed duration of the treatment period?

The treatment period begins at randomisation $(32^{0/7}-38^{6/7})$ weeks gestation) and ends with discharge from hospital following delivery.

2.7. What is the proposed frequency and duration of follow-up?

Following discharge from hospital after the birth, women and infants will be followed for 2 years. The occurrence of a neonatal death or an adverse maternal outcome up to 28 days postpartum will be determined by contacting women and/or their physicians by telephone, mail, or by arranging a clinic or home visit. Women will be contacted at 3 months and asked to complete a structured questionnaire to determine satisfaction with the method of delivery, quality of life, depression, breast feeding, and the occurrence of problematic urinary, faecal or flatal incontinence. Women will be contacted at 2 years after delivery and asked to complete a structured questionnaire to determine the neurodevelopmental outcomes of their children, quality of life, depression, and the presence of problematic urinary, faecal, or flatal incontinence. Questionnaires at 3 months and 2 years following delivery will be completed by mail, if possible, otherwise by telephone or during a clinic or home visit.

2.8. What are the proposed outcome measures?

Because the trial interventions are aimed at managing the mother and her pregnancy, the outcomes are analysed for each set (or cluster) of twins (see section 2.11 for details).

2.8.1 Primary Outcome: Perinatal/neonatal mortality and/or serious neonatal morbidity.

(excluding lethal congenital anomalies)

In order to justify a policy of planned CS, which may increase the risks of maternal mortality and morbidity, there must be an important benefit for the infants. For each twin, perinatal/neonatal mortality and/or serious neonatal morbidity will be defined as one or more of the following during the first 28 days after birth:

- 1. Death (either as stillbirth or as a neonatal death 0 to 27 days after birth)
- 2. Birth trauma defined by any of the following:
 - a. Spinal cord injury
 - b. Basal skull fracture or depressed skull fracture
 - c. Long bone fracture (humerus, radius, ulna, femur, tibia or fibula)
 - d. Peripheral nerve injury (brachial plexus palsies, phrenic nerve palsy, facial nerve palsy) present at 72 hours of age (or at discharge from hospital if sooner)
 - e. Subdural or intracerebral haemorrhage of any kind (confirmed by ultrasound, computerised tomography [CT] scan, magnetic resonance imaging [MRI], or at autopsy)
- 3. Apgar score at 5 minutes less than 4
- 4. Abnormal level of consciousness:
 - a. Coma
 - b. Stupor or decreased response to pain
- 5. Neonatal seizures, defined as clonic movements which cannot be stopped by holding the limb, occurring on two or more occasions before 72 hours of age, regardless of cause
- 6. Need for assisted ventilation \geq 24 hours via endotracheal tube initiated within 72 hours after birth

- 7. Infection within 72 hrs after birth, defined by either of the following:
 - a. Septicemia (positive blood culture)
 - b. Meningitis (positive cerebrospinal fluid culture)
- 8. Necrotising enterocolitis (defined as either perforation of intestine, pneumatosis intestinalis or air in the portal vein) diagnosed by X-ray, surgery, or at autopsy
- 9. Broncho-pulmonary dysplasia (BPD): need for oxygen at a postnatal gestational age of 36 completed weeks + X-ray compatible with BPD
- 10. Intraventricular haemorrhage (IVH): Grade III or IV (diagnosed by cranial ultrasound or at autopsy)
- 11. Cystic periventricular leukomalacia (PVL): Periventricular cystic changes in the white matter excluding subependymal and choroid plexus cysts (diagnosed by cranial ultrasound or at autopsy)

Exclusions for reasons of lethal congenital anomalies will be determined without knowledge of group allocation by an adjudication committee.

2.8.2 Secondary Outcomes:

2.8.2.1 Death or poor neurodevelopmental outcome of the children at 2 years of age (corrected for gestational age at birth)

Neurodevelopmental outcome will be assessed by the Ages and Stages Questionnaire (ASQ).⁴⁹ The ASQ is a parent administered questionnaire, which requires a grade 6 reading level to understand and complete, and has been shown to have a low non-response rate. When necessary, the ASQ can be administered by a professional in a clinic setting rather than by the parent alone at home. Reliability testing in 73 parents and 2 examiners has been found to be very good (97%), with a test-retest agreement at 2 week intervals in 68 parents of 99%. When compared with the Bayley Scales of Infant Development, the sensitivity and specificity for the ASQ at 24 months was 84.5% and 79.3% respectively.⁴⁹ The ASQ is intended to be used as a screening tool, with those infants scoring in the abnormal range being assessed further by experienced health care professionals. For those children scoring low on the ASQ, a formal clinical neurodevelopmental assessment will be performed by a trained professional to determine if the child is normal or abnormal. An abnormal assessment will be defined as the presence of cerebral palsy or a motor or mental developmental delay of more than 3 months. Children with Down Syndrome, Fragile X, or other chromosomal disorders known to contribute to developmental delay (determined by an adjudication committee masked to allocation group) will be excluded. We have used the ASQ successfully in the international multicentre Term Breech Trial and found it to be easy to administer.

2.8.2.2 Problematic urinary or faecal/flatal incontinence of the mothers at 2 years postpartum.

The occurrence of problematic urinary, faecal/flatal incontinence at 2 years following the birth will be determined by structured questionnaire. Mothers will be asked if they have lost or leaked urine when they coughed, laughed or sneezed, etc. (urinary incontinence), if they have lost or leaked faeces/stool, fluid, or mucous unexpectedly from the bowels (faecal incontinence) and/or if they have passed gas/wind unexpectedly from the bowels (flatal incontinence), within the previous 7 days, as well as how much of a problem the incontinence has been (no problem at all, a little problem, a big problem) whether it be urine, stool or flatus. The seven day recall period will capture information on women who are experiencing regular problematic incontinence. A response indicating that the incontinence is causing a little or a big problem will indicate the presence of problematic incontinence. These are similar to the questions that were used in the Term Breech Trial.^{13,32} Women who report problematic incontinence will be asked to complete additional validated questions about the impact of the incontinence, using the IIQ-7.⁵⁰

2.8.3 Other Outcomes:

2.8.3.1 Maternal death or serious maternal morbidity

This is defined as one or more of the following during pregnancy, labour, birth or within the first 28 days following the birth: death; haemorrhage (documented blood loss of \geq 1500cc, blood transfusion required, or need for dilatation/curettage after delivery); laparotomy; genital tract injury (hysterectomy,

vulvar or perineal haematoma requiring evacuation, broad ligament haematoma confirmed by ultrasound, CT or MRI, intraoperative damage to bladder, ureter or bowel requiring repair, fistula involving the genital tract, 3rd or 4th degree perineal tear involving the anal sphincter and/or mucosa); thromboembolism (deep vein thrombosis, thrombophlebitis, or pulmonary embolism) requiring anticoagulant therapy; systemic infection (temperature of 38.5° C or more on 2 occasions at least 24 hours apart not including the first 24 hours, or pneumonia [confirmed by X-ray], or sepsis [confirmed by blood culture]); major medical life threatening illness (eg adult respiratory distress syndrome, amniotic fluid embolism, disseminated intravascular coagulation, bowel obstruction, paralytic ileus [requiring naso-gastric suctioning]); wound infection (requiring prolongation of hospital stay, readmission to hospital or repeated treatment as an outpatient), wound dehiscence or wound breakdown, or other serious maternal complication.

2.8.3.2 Maternal satisfaction with method of delivery:

Determined by the mother's willingness to have the same method of delivery again or recommend it to a friend

- 2.8.3.3 Maternal quality of life: measured by the SF36 51,52
- 2.8.3.4 Maternal fatigue: measured by the Multidimensional Assessment of Fatigue Scale 53
- 2.8.3.5 Maternal depression: measured by the Edinburgh Postnatal Depression Scale ⁵⁴ A score of >12 will indicate depression
- 2.8.3.6 Problematic urinary or faecal/flatal incontinence at 3 months: Women who report problematic incontinence will be asked to complete additional validated questions about the impact of the incontinence, using the IIQ-7.⁵⁰
- 2.8.3.7 Breast feeding

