1.2. What are the principal research questions to be addressed?

1.2.1 Primary Research Question:

For twin pregnancies of $32^{0/7}$ - $38^{6/7}$ weeks gestation, where twin A is presenting cephalic, does a policy of planned CS decrease the likelihood of perinatal or neonatal mortality or serious neonatal morbidity, during the first 28 days after birth, compared to a policy of planned VB?

1.2.2 Secondary Research Questions:

a) For twin pregnancies of $32^{0/7}$ - $38^{6/7}$ weeks gestation, where twin A is presenting cephalic, does a policy of planned CS compared to a policy of planned VB decrease the risk of death or poor neurodevelopmental outcome of the children at 2 years of age, corrected for gestational age at birth?; b) For twin pregnancies of $32^{0/7}$ - $38^{6/7}$ weeks gestation, where twin A is presenting cephalic, does a policy of planned CS compared to a policy of planned VB decrease the risk of problematic urinary or faecal/flatal incontinence for the mother at 2 years postpartum?

1.2.3 Other Research Questions:

For twin pregnancies of $32^{0/7}$ - $38^{6/7}$ weeks gestation, where twin A is presenting cephalic, does a policy of planned CS compared to a policy of planned VB decrease or increase maternal death or serious maternal morbidity (occurring up to 4 weeks following the birth)?; maternal satisfaction with method of delivery determined at 3 months postpartum?; maternal quality of life at 3 months and 2 years postpartum?; maternal depression at 3 months and 2 years postpartum?; breast feeding at 3 months postpartum?; problematic urinary or faecal/flatal incontinence for the mother at 3 months postpartum?; and costs?

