
approach for the delivery of the second twin and document the approach used. We anticipate that over 60% of women in the planned VB group will deliver both twins vaginally.²⁴ If a woman allocated to the planned VB group decides, after randomisation, to be delivered by CS, she should be managed according to the planned CS protocol.

2.3.6 Both Groups:

- a) It should be confirmed that each fetus is alive at the start of labour, before induction of labour and/or before elective CS. If a fetus dies after randomisation and before delivery, the best estimate of the date and time of death should be noted.
- b) Pelvic floor muscle training during pregnancy ⁴⁴⁻⁴⁶ and during the first few months postpartum ^{47, 48} has been shown to reduce the prevalence of postpartum incontinence. All women will therefore be encouraged to undertake pelvic floor muscle exercises and to continue them after delivery.

2.3.7 Schema:

2.4. What are the proposed practical arrangements for allocating participants to the trial groups?

2.4.1 Method of Randomisation:

Randomisation will be centrally controlled using the telephone computerised randomisation service at the University of Toronto Maternal Infant and Reproductive Health Research Unit (MIRU), which centres can access 24 hours per day using a toll-free line. A back up pager system will be maintained at all times to ensure availability of trial staff to handle situations where a technical difficulty is encountered, or where questions arise regarding trial entry. In situations where the automated system fails, hand randomisation will be undertaken.

2.4.2 Timing of randomisation:

Randomisation should ideally be done as close to the time of delivery as possible to minimise contamination. However, women and their caregivers may want time to plan for the delivery and the birth and therefore randomisation may be carried out as early as $32^{0/7}$ weeks gestation if necessary. This may facilitate recruitment into the study. If an eligible woman presents in labour or with an indication for urgent delivery after $32^{0/7}$ weeks but before $39^{0/7}$ weeks gestation and she consents to the trial, she may be randomised.

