2.9. How will outcome measures be measured at follow-up?

Outcomes will be determined by reviewing the hospital medical record following the birth for outcomes occurring prior to the mother's and infants' discharge home. The occurrence of a neonatal death and/or adverse maternal outcome during the first 28 days following the birth after discharge from hospital will be determined by contacting women by telephone, or by home or clinic visit. Satisfaction with the birth experience, breast feeding, problematic urinary/faecal/flatal incontinence and quality of life will be determined by structured questionnaire to be completed by the mother at 3 months (satisfaction, breast feeding, incontinence, quality of life, depression) and 2 years (incontinence, quality of life, depression) following the birth. When children are 2 years of age (corrected for gestational age at birth), the mother or other responsible parent, will be asked to complete an ASQ for each child to assess the neurodevelopment of the children. Questionnaires will be completed ideally by mail; otherwise by telephone or by home or clinic visit. If the ASQ scores in the abnormal range, a formal neurodevelopmental assessment will be arranged.

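### The maternal death or serious morbidity outcome has no start date at randomisation, so as written it can count events that precede allocation (minor)

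*Protocol*

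**What the plan says.** Section 2.8.3.1 of the protocol defines maternal death or serious maternal morbidity as "one or more of the following during pregnancy, labour, birth or within the first 28 days following the birth". The window has a fixed end. Its beginning is the pregnancy, with no date and no reference to randomisation.

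Other sections bear on the window:

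- Section 1.2.3 poses the research question as "maternal death or serious maternal morbidity (occurring up to 4 weeks following the birth", which gives an upper limit only.
- Section 2.6 states: "The treatment period begins at randomisation", that is, at 32 0/7 to 38 6/7 weeks.
- Section 2.4.2 allows randomisation from 32 0/7 weeks but prefers it late: "Randomisation should ideally be done as close to the time of delivery as possible to minimise contamination".
- Section 2.9 gives the source: "Outcomes will be determined by reviewing the hospital medical record following the birth". It sets no lower date.
- Sections 2.5 and 3.3 provide masked adjudication of the neonatal primary outcome, not of maternal events.

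The composite is listed under Section 2.8.3, Other Outcomes. Section 2.16 tests other outcomes at p < 0.01, two-sided.

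**The concern.** A randomised comparison of harm should count only what can happen after allocation. Here most of the pregnancy lies before it. A woman who had, for example, "thromboembolism (deep vein thrombosis, thrombophlebitis, or pulmonary embolism) requiring anticoagulant therapy" at 20 weeks would meet the definition in whichever arm she later joined.

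The consequence is dilution. Events before randomisation add the same expected number to each arm, so the ratio of the odds moves toward 1 and the variance rises. That matters more for a harm outcome than for most others, because the error to avoid is missing a real increase. Section 2.8.1 itself says that planned caesarean section may raise maternal risk, and this composite is where the trial tests that for death and acute serious morbidity.

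**Working it through.** **1. Does the text close the window anywhere?** Sections 1.2.3, 2.6, 2.9, 2.16 and 3.3 were set beside Section 2.8.3.1. None limits maternal events to those after randomisation. The exclusion criteria in Section 2.2.1 do not remove women with earlier maternal morbidity.

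**2. Which components can come before randomisation?** Death cannot. Curettage after delivery, perineal tears and wound complications are tied to birth or surgery. Transfusion, laparotomy, thromboembolism, pneumonia, sepsis, major medical illness and the open category of other serious complications can. Section 2.3.2 also admits women with an indication for urgent delivery such as chorioamnionitis, pre-eclampsia or abruption, so a qualifying event shortly before randomisation is possible.

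**3. How much dilution?** The protocol gives no expected rate, power or sample size for this composite, so there is no plan figure to reproduce. As a check on the method, the same family of formulas gives 1239 per group for the primary outcome (4% vs 2%, 80% power, alpha 0.05, with continuity correction), against 1250 in Section 2.11.

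Inputs:

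- n = 1400 per arm (Section 2.11).
- Two-sided alpha 0.01 (Section 2.16, other outcomes), so z = 2.576.
- 3.2% under planned vaginal birth: the rate in the singleton breech trial cited in Section 1.1.3.2. Its planned caesarean rate was 3.9%.
- 5.6% under planned caesarean: assumed; it is not in the documents.
- q, the share of women with a qualifying event before randomisation: not in the documents; assumed 0.1% to 2%, equal in both arms.

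Formulas, taking the earlier events as independent of the later ones:

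- Observed rate in an arm: p + q − p·q.
- Power = Φ[(d − 2.576·SE0) / SE1], where d is the difference in observed rates, SE0 = √(2·p̄(1 − p̄)/n) with p̄ the mean of the two rates, and SE1 = √{[a(1 − a) + b(1 − b)]/n} for observed rates a and b.

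Example at q = 1%:

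- a = 0.032 + 0.010 − 0.00032 = 0.04168
- b = 0.056 + 0.010 − 0.00056 = 0.06544
- d = 0.02376, SE0 = 0.00851, SE1 = 0.00850
- Power = Φ[(0.02376 − 2.576 × 0.00851)/0.00850] = 58.6%

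| q (both arms) | Women per arm | Odds ratio, 3.2% vs 5.6% | Risk difference (points) | Power, 3.2% vs 5.6% | Power, 3.2% vs 3.9% |
|---|---|---|---|---|---|
| 0 | 0 | 1.79 | 2.40 | 69.9% | 5.8% |
| 0.1% | about 1 | 1.77 | 2.40 | 68.7% | 5.6% |
| 0.5% | 7 | 1.69 | 2.39 | 64.0% | 5.1% |
| 1% | 14 | 1.61 | 2.38 | 58.6% | 4.5% |
| 2% | 28 | 1.50 | 2.35 | 49.3% | 3.8% |

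Two other assumed effects show the same pattern. From q = 0 to q = 2%, power falls from 52.5% to 34.0% at 3.2% vs 5.2%, and from 91.8% to 77.1% at 3.2% vs 6.4%.

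**The case against.** The strongest reply is that the words about pregnancy have a proper use. Randomisation can take place at 32 0/7 weeks and delivery as late as 38 6/7, so several weeks of pregnancy may follow allocation, and a window opening at labour would miss events in them. Read with Section 2.6, with a research question about a policy assigned at randomisation and with the intention-to-treat analysis, the authors may well have meant pregnancy from randomisation onward. This is plausible as intent, but the definition does not say it. Someone completing a form from the hospital record could follow the text and count an earlier event.

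The second reply concerns size, and most of it stands. Many components cannot, or can hardly, precede randomisation. No background rate is given, and the 5.6% is also an assumption. The 2% case means 28 women per arm, against 1400 × 3.2% = 44.8 expected later events in the planned vaginal birth arm; nothing in the documents supports a share that large. At the only maternal rates the protocol cites, power is negligible with or without the fix.

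A reader might infer two stronger claims that the documents do not support:

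- *That this is the trial's only maternal safety comparison.* It is not. "Problematic urinary or faecal/flatal incontinence of the mothers at 2 years postpartum" is a secondary outcome, and incontinence at 3 months and depression are also compared. The composite is the only comparison of maternal death and acute serious morbidity.
- *That the window tilts the result toward one delivery policy.* It does not. Earlier events are balanced in expectation. The ratio is attenuated, but the risk difference moves by only 0.05 of a point even at q = 2%.

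**Conclusion.** The point holds as a minor defect in a rule that the protocol itself fixes. As written, the window opens before randomisation, does not match the treatment period in Section 2.6, and is not closed elsewhere in the protocol. Events before allocation would count although neither policy could have caused them.

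The size is not established. For the assumed 3.2% vs 5.6%, the loss is about 1 power point at a background of 0.1%, 6 at 0.5%, 11 at 1% and 21 at 2%. These figures rest on the assumed caesarean rate, the assumed background, equal background in both arms, and alpha 0.01 applying to this composite because it is listed among the other outcomes. The fall to 49% is the far end of an assumed range and should not be read as the expected effect.

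**What to change.** In Section 2.8.3.1, replace the opening of the window with wording such as: *with onset from randomisation, through labour and birth, to 28 days after the birth*. This keeps the weeks of pregnancy that follow randomisation. Give Section 1.2.3 the same lower limit.

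On the outcome form, record for each qualifying event whether onset was before or after randomisation, or record the onset date. Keep earlier events as baseline history, not as outcomes.

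The cost is one phrase and one extra data field. The field should be in place before data collection, because without onset information earlier and later events may be hard to separate afterwards. Sample size and analysis method do not change.

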2.9. How will outcome measures be measured at follow-up?

Outcomes will be determined by reviewing the hospital medical record following the birth for outcomes occurring prior to the mother's and infants' discharge home. The occurrence of a neonatal death and/or adverse maternal outcome during the first 28 days following the birth after discharge from hospital will be determined by contacting women by telephone, or by home or clinic visit. Satisfaction with the birth experience, breast feeding, problematic urinary/faecal/flatal incontinence and quality of life will be determined by structured questionnaire to be completed by the mother at 3 months (satisfaction, breast feeding, incontinence, quality of life, depression) and 2 years (incontinence, quality of life, depression) following the birth. When children are 2 years of age (corrected for gestational age at birth), the mother or other responsible parent, will be asked to complete an ASQ for each child to assess the neurodevelopment of the children. Questionnaires will be completed ideally by mail; otherwise by telephone or by home or clinic visit. If the ASQ scores in the abnormal range, a formal neurodevelopmental assessment will be arranged.

